## 5.2 EXCLUSION CRITERIA

Patients who meet any of the following criteria will be excluded from the study:

- E 01. Cold agglutinin syndrome secondary to infection, rheumatologic disease, or active hematologic malignancy.
- E 02. History of blood transfusion within 6 months of screening, or history of more than one blood transfusion within 12 months of screening.
- E 03. Clinically relevant infection of any kind within the month preceding enrollment (eg, active hepatitis C, pneumonia).

- E 04. Clinical diagnosis of SLE; or other autoimmune disorders with anti-nuclear antibodies at Screening. Anti-nuclear antibodies of long-standing duration without associated clinical symptoms will be adjudicated on a case-by-case basis during the Confirmatory Review of Patient Eligibility ([Section 6.1.1.3](#)).
- E 05. Positive hepatitis panel (including hepatitis B surface antigen and/or hepatitis C virus antibody) prior to or at Screening.
- E 06. Positive human immunodeficiency virus (HIV) antibody at Screening.
- E 07. Treatment with rituximab monotherapy within 3 months or rituximab combination therapies (eg, with bendamustine, fludarabine, ibrutinib, or cytotoxic drugs) within 6 months prior to enrollment.
- E 08. Concurrent treatment with corticosteroids other than a stable daily dose equivalent to  $\leq 10$  mg/day prednisone for previous 3 months.
- E 09. Erythropoietin deficiency. Concurrent treatment with erythropoietin is permitted if the patient has been on a stable dose for the previous 3 months.
- E 10. Concurrent usage of iron supplementation unless the patient has been on a stable dose for at least 4 weeks.
- E 11. Clinically significant medical history or ongoing chronic illness that would jeopardize the safety of the patient or compromise the quality of the data derived from his/her participation in this study (as determined by the Investigator [or designee]) at Screening.
- E 12. Concurrent treatment with other experimental drugs or participation in another clinical trial with any investigational drug within 30 days or 5 half-lives, whichever is greater, prior to treatment start.
- E 13. Females who are pregnant, lactating, or, if having reproductive potential, are considered potentially unreliable with respect to contraceptive practice.
- E 14. History of hypersensitivity to BIVV009 or any of its components.

For home infusion in/exclusion criteria see ([Appendix K](#)).

For undiluted infusion eligibility criteria see [Section 4.1](#).

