SLE panel will be summarized with descriptive statistics. The number of subjects with all negative or all missing values for all SLE panel parameters prior to receiving study drug and the number of subjects with at least one positive value for at least one SLE panel parameter prior to receiving study drug will be summarized. Further, among subjects who have all negative or all missing values for all SLE parameters prior to receiving study drug and have at least one post-baseline value for at least one parameter, the number of subjects who test negative at all post-baseline assessments for all SLE parameters, and the number of subjects who test positive at any post-baseline assessment for at least one SLE parameter will be summarized.

Similar summaries will be generated for individual SLE parameters. In addition, for a given SLE parameter, among subjects who have at least one positive or all missing values prior to receiving study drug and have at least one post-baseline for this parameter, the number of subjects who test positive at all post-baseline assessments, and the number of subjects who test negative at any post-baseline assessment will be summarized.

Parameters in the SLE Panel are Antinuclear antibody (ANA), multiplex with dsDNA, Anti-La/SSB antibody (SS-B), Anti-ribonucleoprotein antibody (RNP), Anti-Smith antibody (Sm), Anti-Ro/SSA antibody (SS A), Anti-scleroderma antibody (Scl-70), Anti-Chromatin antibody, Anti-Jo-1 antibody, Anti-Centromere B antibody, Circulating immune complexes (CIC).

Disease-Related Biomarkers

Disease-related biomarkers include DAT (polyspecific, anti-IgG & anti-C3d), LDH isoforms, cold agglutinin (CAG) titre, IgG subsets (IgA, IgD, IgG, IgM), vaccine titres, CAG thermal amplitude. Actual values and change from baseline for all biomarkers will be summarized by visit by treatment arm.

Electrocardiogram (ECG)

The proportion of subjects with clinically significant change from baseline in ECG findings will be summarized by visit.

Vital Signs

Vital signs (systolic and diastolic blood pressure, pulse, respiratory rate, and temperature) will be summarized for the observed values and change from baseline using descriptive statistics for the Safety Analysis Set.

The number and percentage of subjects with potentially clinically relevant post-baseline abnormalities will be presented. The criteria for clinically relevant post-baseline abnormalities are shown below in [Table 12](#).

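### In the per-parameter SLE summaries of both SAPs, a patient with no pre-dose result is placed in both baseline groups and so is counted among baseline positives without an observed positive.

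*SAP*

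**What the plan says.** The SLE paragraphs of section 4.7.3.1 read the same in the Part A and Part B SAPs and work in three steps.

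- **Whole panel, before dosing.** One count covers patients with nothing but negative or missing values. The other is "the number of subjects with at least one positive value for at least one SLE panel parameter". Missing values sit on the negative side only.
- **Whole panel, after dosing.** "among subjects who have all negative or all missing values for all SLE parameters prior to receiving study drug", and given at least one post-baseline value, the SAP reports "the number of subjects who test negative at all post-baseline assessments for all SLE parameters", alongside a count of those with any later positive result on any parameter.
- **Each parameter.** "Similar summaries will be generated for individual SLE parameters", which brings the negative-or-missing group down to parameter level. A second group is then added for each parameter, "among subjects who have at least one positive or all missing values prior to receiving study drug", again with a post-baseline value required. For it the SAP reports "the number of subjects who test positive at all post-baseline assessments, and the number of subjects who test negative at any post-baseline assessment".

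Neither SAP says what to do with a patient who meets both per-parameter definitions, and neither defines a missing-baseline category for this panel.

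**The concern.** A positive/negative test gives a patient one baseline state for each parameter. The first per-parameter group answers how many patients without a known positive became positive. The second answers what happened to those who were already positive. A patient with no pre-dose value gives no information on the second question, yet is counted in it. If the post-dose result is positive, the patient adds to the count of those positive throughout. If it is negative, the patient adds to the count of those who turned negative, which looks like a favourable change from a positive baseline that nobody observed.

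SLE serology matters in this trial. Protocol section 2.2.4 raises lupus as a theoretical risk of long-term C1s inhibition and builds the markers in as surveillance. Change from baseline in the panel is a safety endpoint (Protocol section 4.3.5) and falls under the primary objective of Part B (SAP Part B, Table 2). Baseline-positive groups are likely to be small, so one wrongly placed patient can be visible in the table.

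**Working it through.** The plan states no figure on this point, so there is nothing to reproduce. The check applies the counting rules to every possible case for one parameter.

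**Inputs.** The group and outcome rules of SAP section 4.7.3.1; about 40 patients, 20 per arm (Part A SAP section 2); and the panel schedule, which is screening, Week 26, every 6 months in Part B, and the early termination/end-of-study visit (Protocol Table 3). The number without a pre-dose value (m) and the number of observed baseline positives (k) are not in the documents and are assumed.

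**Step 1: enumerate.** Group 1 is negative or no result; group 2 is positive or no result. The short outcome labels are mine.

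| Pre-dose | Post-baseline results | Group 1 cell | Group 2 cell |
|---|---|---|---|
| negative | all negative | never positive | none |
| negative | any positive | ever positive | none |
| positive | all positive | none | always positive |
| positive | any negative | none | ever negative |
| no result | all positive | ever positive | always positive |
| no result | all negative | never positive | ever negative |
| no result | mixed | ever positive | ever negative |

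A patient with a known baseline always falls in one cell; a patient without one always falls in two. Part A normally gives a single post-baseline result, so the mixed row arises mainly in Part B.

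**Step 2: check where the overlap stops.** At whole-panel level the negative-or-missing count and the at-least-one-positive count cannot share a patient, because missing is never placed with positive. The same holds for the pre-dose counts. The overlap is confined to the per-parameter post-baseline tables.

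**Step 3: denominators.** Take 40 patients, all with a post-baseline value.

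- As written, the two group sizes sum to 40 + m: 41 when m = 1, 44 when m = 4.
- With no-result patients in their own row, the two groups sum to 40 − m and the row holds m: 39 + 1 when m = 1, 36 + 4 when m = 4. Each patient is counted once.

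**Step 4: weight of one patient in group 2.** With k observed positives, one no-result patient is 1/(k + 1) of the group:

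- k = 0: 1/1 = 100%
- k = 1: 1/2 = 50%
- k = 4: 1/5 = 20%

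**The case against.** The best defence is that the overlap is a deliberate convention. In the same section, the haematology and chemistry shift tables keep an unknown baseline at risk for a shift to low and for a shift to high, and patients with no baseline enter the abnormality numerator. Section 4.7.2 counts an adverse event of unknown relationship as related. The SLE groups may likewise be two at-risk sets that nobody intends to add up, and the SAP never uses words such as persistent or reverted.

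Part of this stands. Keeping a missing baseline with the negatives is the cautious choice, because a post-dose positive then stays in the count that matters for safety. A reader might infer that this placement is unsafe; it errs in the protective direction. The defence does not cover the second group. In a shift table a normal baseline really is at risk in both directions, whereas no known SLE result belongs to both groups, and placing an unknown with the positives protects nobody.

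Other stronger readings also fail:

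- **Exclusion E 04.** It says that "Anti-nuclear antibodies of long-standing duration without associated clinical symptoms will be adjudicated on a case-by-case basis", and a reader might infer that missing baselines hide antibody-positive patients. A patient admitted by that route has a known antinuclear antibody result and would be classed as positive, not missing.
- **A lost screening sample.** A reader might infer that it cannot be replaced, since the panel is not on the Day 0 list. The Laboratory Tests paragraph of Protocol section 6.1.1.1 allows one repeat at the investigator's discretion and more with sponsor approval.

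It is also fair that the summaries are descriptive, that the panel is a scheduled screening test, and that the listings required by Protocol section 7.1 would show a missing value.

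**Conclusion.** The point holds, for the per-parameter SLE tables only, in both SAPs. It rests on reading the instruction to produce similar summaries as carrying the negative-or-missing rule down to each parameter, which is the natural reading. It does not depend on any assumption about how much is missing: following the text counts every no-result patient who has a post-baseline value twice, once among baseline positives with no observed positive.

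The practical size is small and cannot be fixed from the documents, because m and k are not given. A reader might take one patient in 20 (5 points) or one in 40 (2.5 points) as the most that can happen. That is not a bound, because the denominators are baseline subgroups: in a first group with 10 observed negatives, 0/10 becomes 1/11, or 9.1%, and in the second group the share is 1/(k + 1). No hypothesis test or efficacy result is affected. This is a minor correction worth making because it costs almost nothing.

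**What to change.** In section 4.7.3.1 of both SAPs:

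1. Remove the words *or all missing* from the definition of the second per-parameter group, so that it holds only patients with an observed pre-dose positive for that parameter.
2. Show patients with no pre-dose result for the parameter in a separate row, with their own counts of positive and negative post-baseline results.

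The separate row needs its outcome counts. Simply excluding these patients could remove a post-dose positive from view, which would be worse for surveillance than the present overlap.

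The cost is one sentence in each SAP and one row in the table shells. The baseline-positive denominator becomes smaller by the number of patients who had no observed positive, which is the intended effect. No new data are needed.

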4.8 OTHER ANALYSES

4.8.1 PK Analyses

Plasma BIVV009 concentrations will be listed by subject, nominal visit, date and time of collection and study day. Summary statistics of plasma BIVV009 concentrations will be presented by nominal visit and study day including n, mean, standard deviation, coefficient of variation, geometric mean, median and range stratified by dose cohort (6.5 g vs 7.5 g) for the BIVV009 treatment arm. Individual and mean plasma BIVV009 concentration-versus-time profiles will be plotted.

4.8.2 PD Analyses

Descriptive statistics including number of observations, mean, SD, median, minimum, and maximum will be presented for continuous parameters. Categorical variables will be presented with the number and percentage in each category. Summary descriptive statistics (absolute values and changes from baseline) and individual subject listings will be presented for all PD parameters by time point and study day for both the BIVV009 and Placebo treatment arms.

4.9 INTERIM ANALYSES

For the purposes of regulatory submission, an interim analysis of safety and efficacy data (Part A analysis) will be performed for Part A after all patients have completed Part A and the data are cleaned. Parts A and B will have separate database locks to enable submission of the MAA following completion of Part A. Additional analyses of Part B data will be defined in a separate Part B SAP.

Since Part A analysis constitutes the primary analysis of the study hypotheses, no Type I error adjustment is necessary.

5 SUPPORTING DOCUMENTATION

5.1 APPENDIX 1 LIST OF ABBREVIATIONS

AE	adverse event
ADL	activities to daily living
ALP	alkaline phosphatase
ALT	alanine aminotransferase
ANA	antinuclear antibodies
AST	aspartate aminotransferase
AUC	area under the curve
BLA	Biologics License Applications
BUN	blood urea nitrogen
CAGD	cold agglutinin disease
CI	confidence interval
CIC	circulating immune complexes
C _{max}	maximum concentration
CTCAE	Common Toxicity Criteria for Adverse Events
DBL	database lock
ECG	electrocardiogram
eCRF	electronic Case Report Form
EOT	end of treatment
EQ-5D-5L	EuroQol – five dimensions questionnaire
ET	early termination
FACIT	functional assessment of chronic illness therapy
FAS	full analysis set
GGT	gamma-glutamyl transferase
Hgb	hemoglobin
HUI	health utility index
ICE	intercurrent events
ICH	International Conference of Harmonisation
ITT	intent-to-treat
IV	intravenous
LDH	lactate dehydrogenase
LLN	lower limit of normal
LPO	last patient out
MAA	Marketing Authorization Application
MAR	missing at random
MCMC	Markov chain Monte-Carlo
MedDRA	Medical Dictionary for Regulatory Activities
MMRM	Mixed Model for Repeated Measures
MNAR	Missing Not At Random
NRC	National Research Counsel
PD	pharmacodynamics
PGIC	Patient's Global Impression of Change

PGIS	Patient’s Global Impression of Severity
PK	pharmacokinetics
PP	per-protocol
PRO	patient-reported outcome
QOL	quality of life
RBC	red blood cell count
SAE	serious adverse event
SAP	Statistical Analysis Plan
SD	standard deviation
SF-12	12-Item Short Form Survey
SGOT	serum glutamic oxaloacetic transaminase
SGPT	Serum glutamic-pyruvate transaminase
SLE	systemic lupus erythematosus
SOC	system organ class
TEAE	treatment-emergent adverse event
TLF	tables, figures, and listings
TOEPH	heterogeneous Toeplitz
ULN	upper limit of normal
WBC	white blood cell count

5.2 APPENDIX 2 CHANGES TO PROTOCOL-PLANNED ANALYSES

This section summarizes major statistical changes in the protocol amendment(s).

Table 13 - Major statistical changes in protocol amendment(s)

Amendment Number	Approval Date	Changes	Rationale
Version 1 (original)	24-Aug-2017	Not applicable	Not applicable

5.3 APPENDIX 3 DEMOGRAPHICS AND BASELINE CHARACTERISTICS, PRIOR OR CONCOMITANT MEDICATIONS

Demographics and baseline disease characteristics will be summarized for the FAS.

Demography

Demographic characteristics including age (years), age category (<65, ≥65), gender, race, ethnicity, country, geographic location, height (cm), weight (kg), weight category (<75 kg, ≥75 kg), and body mass index (kg/m²) will be summarized. Geographic locations are defined as Europe, North America, Asia/Japan, and other.

General Medical History

Medical history by system organ class (SOC) and preferred term (PT) will be summarized. A subject will be counted only once if they reported one or more occurrences in the same SOC or PT.

A summary of prior hospitalizations related to CAD within the last 2 years, prior hematological malignancies within the last 5 years, prior non-malignant hematologic diseases within the last 5 years, and prior thromboembolic events within the last 1 year will be presented based off the “Targeted Medical History” eCRF form.

Baseline Disease Characteristics

Screening and baseline lab parameters, including hematology (such as Hgb, bilirubin, LDH), Gilbert’s Syndrome testing, and bone marrow biopsy results will be summarized. Prior transfusion history (eg, number of transfusions within 12 months of study entry) will also be summarized.

Severity of anemia symptoms and other CAD-related disease characteristics (eg, presence of acrocyanosis, Raynaud’s syndrome, hemoglobinuria, disabling circulatory symptoms, and major adverse vascular events) within 3 months of screening will be summarized.

The proportion of subjects who had documented vaccines within 5 years and who have received vaccination during the study will be summarized. The vaccines include meningococcal vaccine, S. pneumoniae vaccine, and H. influenza vaccine.

Prior or concomitant medications

Prior medications are those taken before the first dose of study drug in Part A. Concomitant medications are those administered on or after the first dose of study drug, or those administered before the first dose that are ongoing when study treatment begins. Prior and concomitant medications will be coded using World Health Organization drug enhanced dictionary (March 2020 version or higher).

Separate tables will be generated to summarize concomitant medications and concomitant protocol-prohibited medications by ATC level 2 and WHODrug standardized medication text.

Additionally, a summary of targeted prior therapies will be generated based off the responses provided in the “Targeted Prior Therapy” eCRF form.

Concomitant non-drug treatments and procedures

Concomitant non-drug treatments and procedures will be summarized for the FAS.

5.4 APPENDIX 4 DATA HANDLING CONVENTIONS

Study Day

Study Day is defined as days relative to the date of first dose of study drug (BIVV009 or placebo) in Part A (Day 0 as in the protocol). The Study Day of an event is calculated as

- (date of event – date of first dose of study drug in Part A + 1), if the event is on or after the first dose date;
- (date of event – date of first dose of study drug in Part A), if the event is prior to the first dose date.

The date of the first dose of study drug in Part A is Study Day 1.

Baseline

Baseline measures are defined as the last value prior to the first dose of study drug. If a subject receives a transfusion during the screening period, the baseline measure must be at least 7 days after the transfusion.

Visit Windows

Analysis by study visit will utilize the data recorded on the corresponding nominal visit from electronic Case Report Forms (eCRFs). In case of missing data/assessments for a visit, data from an unscheduled visit, or ET/Safety Follow-up Visit will be used, if the Study Day of such a visit fits in the analytic window defined in [Table 14](#), below. If multiple values are identified within the analytic window, the one closest to the target study day will be used.

[figure not shown]
Table 14 - Analyses window definition

[figure not shown]
Visit	Target Study Day	Analytic Visit Window
Baseline (Day 0)	1	≤1
Week 1 (Day 7)	8	2 – 15
Week 3 (Day 21)	22	16 – 29
Week 5 (Day 35)	36	30 – 43
Week 7 (Day 49)	50	44 – 57
Week 9 (Day 63)	64	58 – 71
Week 11 (Day 77)	78	72 – 85
Week 13 (Day 91)	92	86 – 99
Week 15 (Day 105)	106	100 – 113
Week 17 (Day 119)	120	114 – 127
Week 19 (Day 133)	134	128 – 141
Week 21 (Day 147)	148	142 – 155
Week 23 (Day 161)	162	156 – 169
Week 26 (Day 175)	176	170 – 179
Week 26 (Day 182; EOT Visit in Part A)	183	180 – 189

5.5 APPENDIX 5 PATIENT-REPORTED OUTCOMES

[figure not shown]
5.5.1 Scoring algorithm for FACIT-F

[figure not shown]
Figure 1 - FACIT-Fatigue Scale

[figure not shown]

[figure not shown]
5.5.2 EQ-5D-5L questionnaire score definitions

[figure not shown]

[figure not shown]
5.5.3 12-item short form survey (SF-12)

1 INTRODUCTION

1.1 STUDY DESIGN

BIVV009-04 is a Phase 3, randomized, double-blinded, placebo-controlled, multicenter study in patients with primary cold agglutinin disease (CAD) without a recent history of blood transfusion. Eligible patients received study drug (BIVV009 or placebo) and underwent safety and efficacy assessments for 6 months (26 weeks) in Part A of the study.

Following completion of the initial 6-month treatment period, patients will roll into the long-term safety study (Part B) where they will continue to receive the study drug, BIVV009. After completion of all Part A EOT assessments, patients who qualify to roll-over into Part B will receive a cross-over loading dose, in a blinded manner, at the Week 26 visit. Patients who were randomized to placebo during the 6-month treatment period will receive BIVV009; and patients who were randomized to BIVV009 during the 6-month treatment period will receive a placebo dose in order to maintain the blinding. Part B will run for one year following last patient out (LPO) under Part A. In Part B, patients will be dosed with open-label BIVV009 every two weeks, as in Part A. On-site visits will be completed every two weeks when samples for safety and efficacy measures will be collected; samples for pharmacokinetics (PK) and pharmacodynamics (PD) will be collected at visits approximately every three months. Sample for antidrug antibodies will be collected every three months (at a minimum). The study will be complete 12 months following LPO under Part A at which time all patients receiving on-going treatment will proceed to an End-of-Study (EOS) visit 9 weeks after the last administration of study drug.

After Week 39, a subgroup of patients will have their study drug infused at home, every four weeks, alternating with study drug administration during office visits. Additionally, after Week 39, another subgroup of patients will have their study drug administered in the form of infusions undiluted with normal saline.

Study primary analysis will be conducted for Part B after all patients have completed Part B and the data are cleaned.

This statistical analysis plan contains information pertaining to definitions of analysis sets and derived variables, and statistical methods for the analysis of efficacy, safety, PK, and PD for Part B of the referenced study.

